3.0 Patient Eligibility

- 3.1 Inclusion Criteria
 - 3.11 Age \geq 18 years.
 - 3.12 Histologic or cytologic confirmation of lung cancer (squamous, Rasmutated adenocarcinoma or small cell lung cancer).
 - 3.13 Patients must have received at least one course of chemotherapy consisting of a platinum doublet and must have no acceptable standard treatment options.
 - 3.14 Prior radiation therapy is permitted as long as:
 - Recovered from the toxic effects of radiation treatment before study entry, except for alopecia.
 - 3.15 The following laboratory values obtained \leq 14 days prior to registration:
 - ANC >1500 □L
 - PLT ≥100,000 □L
 - Hgb ≥9 g/dL
 - Total bilirubin ≤1.5 x upper limit of normal (ULN) or direct bilirubin <ULN
 - SGOT (AST) and SGPT (ALT) □3 x ULN or SGOT (AST) and SGPT (ALT) □5 x ULN is acceptable if liver has tumor involvement
 - 3.16 ECOG performance status (PS) 0, 1, 2. (Appendix I)

| | 3.17 | Negative serum pregnancy test done \leq 7 days prior to registration, for women of childbearing potential only. |
|-----|--------|--|
| | 3.18 | Ability to provide informed consent. |
| | 3.19a | Life expectancy □12 weeks. |
| | 3.19b | Willing to return to Mayo Clinic enrolling institution for follow-up. |
| | 3.19c | Willing to provide tissue samples for correlative research purposes (see Sections 6, 17). |
| 3.2 | Exclus | sion Criteria |
| | 3.21 | Any of the following because this study involves an agent that has known genotoxic, mutagenic and teratogenic effects. Pregnant women Nursing women Men or women of childbearing potential who are unwilling to employ adequate contraception |
| | 3.22 | Symptomatic, untreated, or uncontrolled CNS metastases or seizure disorder. NOTE: Patients with treated CNS metastases without evidence of progression and without uncontrolled symptoms or need for steroids may enroll. |
| | 3.23 | HIV-positive patients receiving combination anti-retroviral therapy are excluded because of possible pharmacokinetic interactions with oral investigational agents. |
| | 3.24 | Unwilling or unable to, comply with the protocol. |
| | 3.25 | Any of the following prior therapies: ☐ Radiation to ≥25% of bone marrow (see appendix III) |
| | | ☐ Major surgery (i.e., laparotomy), open biopsy, or significant traumatic injury ≤4 weeks prior to registration. Minor surgery ≤2 weeks prior to registration. Insertion of a vascular access device is not considered major or minor surgery in this regard. |

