10.13 Assessment of Attribution

When assessing whether an adverse event is related to a medical treatment or procedure, the following attribution categories are utilized:

Definite - The adverse event *is clearly related* to the investigational agent(s). Probable - The adverse event *is likely related* to the investigational agent(s).

Possible - The adverse event *may be related* to the investigational agent(s).

Unlikely - The adverse event *is doubtfully related* to the investigational agent(s).

Unrelated - The adverse event *is clearly NOT related* to the investigational agent(s)

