10.2 Expedited Adverse Event Reporting Requirements

10.21 Paper reporting will be done via the AdEERS form found at Adverse Event Expedited Report – Single Agent or Multiple Agents

| | Grade 4 or 5 ¹ Unexpected/ Expected Regardless of Attribution | Grade 3 Unexpected/ Expected Regardless of Attribution | Other Grade 4 or 5 Events and/or any Hospitalization During Treatment Not Otherwise Warranting an Expedited Report |
|---|--|--|--|
| Submit written report within 5 working days ² | X | X | |
| Submit Grade 4 or 5 Non-AER Reportable Events/Hospitalization in EDC within 5 working days. ³ | | | X^3 |

- 1. Includes all deaths within 30 days of the last dose of agent regardless of attribution or any death attributed to the agent(s) (possible, probable, or definite) regardless of timeframe.
- 2. Use paper *Adverse Event Expedited Report Single Agent or Multiple Agents* report available within the study forms packet

.

Mayo Clinic Cancer Center (MCCC) Institutions: Provide copies, along with the UPIRTSO cover sheet, by [contact]) to the MCCC Regulatory Affairs Unit (RAU) Risk Information Specialist who will determine and complete IRB reporting. The RAU will submit to the MCCC SAE Coordinator and the MCCC IND Coordinator to determine if FDA submission is needed.

3. Complete a Notification Form: Grade 4 or 5 Non-AER Reportable Events/Hospitalization Form electronically via the Data Entry System within 5 working days of the date the clinical research associate (CRA) is aware of the event(s) necessitating the form. If expedited written report was submitted, this form does not need to be completed.

10.3 Adverse events to be graded at each evaluation and pretreatment symptoms/conditions to be evaluated at baseline per the CTCAE v4.0 grading unless otherwise stated in the table below:

| System Organ Class (SOC) | Adverse event/Symptoms | Baseline | Each evaluation |
|--|----------------------------|----------|-----------------|
| General disorders and administration site conditions | Fever | X | X |
| Blood and lymphatics system disorders | Anemia | X | X |
| Investigations | Neutrophil count decreased | X | X |
| | Platelet count decreased | X | X |
| | Creatinine increased | X | X |
| | | X | X |
| | Cholesterol high | X | X |
| | Blood bilirubin increased | | |
| Vascular disorders | Hypotension | X | X |
| | Flushing | X | X |
| Skin and Subcutaneous tissue orders | Rash Acneiform | X | X |
| Gastrointestinal disorders | # of stools | X | |

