| | Diarrhea | | X |
| | Nausea | X | X |
| | Vomiting | X | X |
| | Mucositis, oral | X | X |

| Infections and | Bladder Infection | X | X |
|-----------------------------------|----------------------|---|---|
| Infestations | Bronchial Infection | X | X |
| | Skin Infection | X | X |
| | Lung Infection | X | X |
| Renal and urinary disorders | Proteinuria | X | X |
| Metabolism and | Hyperglycemia | X | X |
| Nutrition disorders | Hypertriglyceridemia | X | X |
| Musculoskeletal | Myalgia | X | X |
| and connective tissue disorders | Arthralgia | X | X |
| Nervous system disorders | Dizziness | X | Х |
| Immune system disorders | Allergic Reaction | X | X |

- 10.31 Submit via appropriate MCCC Case Report Forms (i.e., paper or electronic, as applicable) the following AEs experienced by a patient and not specified in Section 10.3:
 - 10.311 Grade 2 AEs deemed *possibly, probably, or definitely* related to the study treatment or procedure.
 - 10.312 Grade 3 and 4 AEs regardless of attribution to the study treatment or procedure.
 - 10.313 Grade 5 AEs (Deaths)
 - 10.3131 Any death within 30 days of the patient's last study treatment or procedure regardless of attribution to the study treatment or procedure.

- 10.3132 Any death more than 30 days after the patient's last study treatment or procedure that is felt to be at least possibly treatment related must also be submitted as a Grade 5 AE, with a CTCAE type and attribution assigned.
- 10.32 Refer to the instructions in the Forms Packet (or electronic data entry screens, as applicable) regarding the submission of late occurring AEs following completion of the Active Monitoring Phase (i.e., compliance with Test Schedule in Section 4.0).

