14.0 Body Fluid Biospecimens: None

15.0 Drug Information

15.1 Auranofin for Oral Administration (Ridaura®)

- 15.11 **Background**: Auranofin is a gold compound which has antiinflammatory effects. Gold compounds can alter the immune response and have been shown to inhibit prostaglandin synthesis.
- 15.12 **Formulation**: Commercially available for oral administration as: Capsules: 3 mg [gold 29%]

- 15.13 **Preparation, storage, and stability**: Refer to package insert for complete preparation and dispensing instructions. Store oral tablets at room temperature. Dispense in a tight, light-resistant container.
- 15.14 **Administration:** Refer to the treatment section for specific administration instructions.

15.15 Pharmacokinetic information:

Absorption: ~25% of the gold in a dose of Auranofin is absorbed from the gastrointestinal tract

Protein binding: Moderate. In blood, approximately 60% of the gold is bound to plasma proteins; the remainder is present in red blood cells

Metabolism: Rapidly metabolized (the intact molecule has not been detected in blood)

Half-life elimination: Blood: 21 - 31 days. Tissue: 42 - 128 days **Excretion**: 60% of the absorbed gold (15% of the administered dose) is excreted in the urine; the remainder of the dose is excreted in the feces

15.16 Potential Drug Interactions:

In a single patient-report, there is the suggestion that concurrent administration of Auranofin and phenytoin may have increased phenytoin blood levels.

15.17 **Known potential adverse events:** Consult the package insert for the most current and complete information. Auranofin is contraindicated in patients with a history of any gold-induced disorders: anaphylactic reactions, necrotizing enterocolitis, pulmonary fibrosis, exfoliative dermatitis, bone marrow aplasia or other severe hematologic disorders.

Common known potential toxicities, > 10%:

Dermatologic: Dermatitis (aggravated by sunlight), pruritus, actinic rash, hair loss, urticaria

Gastrointestinal: Nausea, vomiting, abdominal cramps, diarrhea, loose stools, constipation, dysgeusia, stomatitis, glossitis Hematologic: Anemia, leukopenia, thrombocytopenia, Eosinophilia

Hepatic: Elevated liver enzymes

Renal: Hematuria

Less common known potential toxicities, 1% - 10%:

Gastrointestinal: Anorexia, flatulence, dyspepsia

Ocular: Conjunctivitis Renal: Proteinuria

Rare known potential toxicities, <1% (Limited to important or life-threatening):

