16.21 Adverse Events Profile

The number and severity of all adverse events (overall and by dose level) will be tabulated and summarized.

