Adverse Events: All eligible patients that have initiated treatment will be considered evaluable for assessing adverse event rate(s). The maximum grade for each type of adverse event will be recorded for each patient, and frequency tables will be reviewed to determine patterns. Additionally, the relationship of the adverse event(s) to the study treatment will be taken into consideration.

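### The adverse event tables make no use of the mandatory baseline grades, so unchanged low-grade entry conditions can be counted in the single-arm safety profile

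*Combined protocol and SAP*

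**What the plan says.** **Baseline collection.** Section 6.38 makes baseline grading compulsory. Section 10.3 lists the solicited items, with "pretreatment symptoms/conditions to be evaluated at baseline per the CTCAE v4.0 grading unless otherwise stated", and has the same items graded at each evaluation. Diarrhea is the exception: a stool count is taken at baseline and diarrhea is graded on treatment. Section 18.0 provides a Baseline Adverse Event Form.

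**Which events reach the database.** The rule in Section 10.311, under which Grade 2 events are submitted only if at least possibly related, applies to "the following AEs experienced by a patient and not specified in Section 10.3". It does not screen the solicited items.

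**Analysis.** Section 16.52: "The maximum grade for each type of adverse event will be recorded for each patient, and frequency tables will be reviewed to determine patterns". The next sentence adds that relationship to treatment will be considered, without saying how. Section 16.21, for phase I: "The number and severity of all adverse events (overall and by dose level) will be tabulated and summarized". Neither section mentions the baseline grade, defines a new or worsened event, or says whether the maximum leaves out the baseline record. The translational part of Section 16.52 also relates gene amplification and protein expression to adverse event incidence, with no grade, attribution or baseline rule.

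**Who may enter.** Section 3.15 admits hemoglobin down to 9 g/dL and "Total bilirubin ≤1.5 x upper limit of normal (ULN) or direct bilirubin <ULN". Anemia and raised bilirubin are both solicited items. Section 3.26 excludes raised lipids only from Grade 2 upward.

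**The concern.** Taken literally, a maximum-grade rule over repeated gradings counts a condition that was present before treatment and never changed. The patients are pretreated with platinum chemotherapy and may have performance status 2, so some low-grade abnormalities at entry are to be expected.

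The adverse event profile is a stated secondary goal (2.22). With no control arm, each patient's own baseline is the only background reference in the trial. If it is not used, any-grade and low-grade rates of the solicited items can mix entry conditions with events that arose or worsened on treatment. In the phase I tables by dose level, with three to six patients per level, one carried-over condition moves a rate by 17 to 33 percentage points (1/6 to 1/3).

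**Working it through.** The plan states no figure on this point, so there is nothing to reproduce. The check has two parts.

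**1. Do the documents contain a baseline rule?** The sections on collection (4.0, 6.38, 10.3, 10.31, 18.0) and on analysis (16.11, 16.2, 16.52, 16.532) were compared. The reference data are collected, but no analysis section uses them. The nearest substitute is attribution (10.13), which asks about cause and not about change. The two can differ. Section 15.17 lists under auranofin toxicities above 10% "Hematologic: Anemia, leukopenia, thrombocytopenia, Eosinophilia", so an investigator could reasonably score an unchanged anemia as Possible. Another could score it as Unlikely.

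**2. How large could the effect be?** This is an illustration under assumed values. Let

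- p = true risk of a new or worsened event. Take 10%, the lower edge of the category in 15.17 that contains anemia.
- q = share entering with the condition (assumed, independent of p).
- r = share of unchanged entry conditions that stay in the table, i.e. are re-recorded and not removed by attribution (assumed).
- n = 41, the maximum in the efficacy portion (16.12). The adverse event set is all eligible patients who started treatment (16.52), not the 37 of the efficacy decision rule. The overall maximum is 47.

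Tabulated rate = p + (1 − p)·q·r. For example, with q = 30% and r = 0.5: 0.10 + 0.90 × 0.30 × 0.5 = 0.235, and 41 × 0.235 = 9.6 patients.

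| q | r = 1 | r = 0.5 | r = 0.25 |
|---|---|---|---|
| 10% | 19% (7.8) | 14.5% (5.9) | 12.3% (5.0) |
| 20% | 28% (11.5) | 19% (7.8) | 14.5% (5.9) |
| 30% | 37% (15.2) | 23.5% (9.6) | 16.8% (6.9) |
| 50% | 55% (22.6) | 32.5% (13.3) | 21.3% (8.7) |

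Expected patients out of 41 are in brackets, against 41 × 0.10 = 4.1 with a new or worsened event. With 47 patients the counts at q = 30% are 17.4, 11.0 and 7.9, against 4.7. For commoner events the relative effect is smaller. At p = 30%, over the same q, the ratio of tabulated to true rate is 1.2 to 2.2 (r = 1), 1.1 to 1.6 (r = 0.5) and 1.1 to 1.3 (r = 0.25).

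**Compared with sampling error.** With n = 41, find the smallest count whose exact (Clopper-Pearson) 95% interval lies wholly above the true p:

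- p = 10%: 9 patients (22.0%, interval 10.6 to 37.6%)
- p = 20%: 14 patients (34.1%, interval 20.1 to 50.6%)
- p = 30%: 19 patients (46.3%, interval 30.7 to 62.6%)

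The chance of reaching that count, from the binomial distribution with probability p + (1 − p)·qr, is:

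| qr | p = 10% | p = 20% | p = 30% |
|---|---|---|---|
| 0 | 2% | 2% | 2% |
| 5% | 13% | 9% | 6% |
| 10% | 37% | 24% | 14% |
| 15% | 65% | 44% | 27% |
| 20% | 85% | 65% | 44% |

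Carry-over of 5% is hard to tell from noise. Carry-over of 15 to 20% is visible for uncommon events and less so for common ones. The plan proposes no confidence interval for adverse event rates; the interval serves here only as a yardstick.

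**The case against.** The strongest reply is that silence is not a counting rule. Section 10.3 distinguishes adverse events on treatment from pretreatment conditions, and baseline grades have their own form. How an unchanged condition is entered on the on-treatment form may be settled in the Forms Packet, which is not in the documents. This stands as a limit on size: r cannot be known from here. It does not supply the missing rule, since the analysis sections are where a rule for the tables belongs.

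Second, the plan already reduces the problem. Attribution will be considered, Grade 2 lipid elevation is excluded at entry, diarrhea has a baseline stool count, and unlisted Grade 2 events are screened for relatedness. All of this is true, and it narrows the point to low grades of the solicited items. For lipids only Grade 1 is affected.

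Third, the tables are descriptive, with no test or threshold attached. That is also true and sets the weight of the point.

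A reader might infer more, in three ways that the documents do not support.

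- *That dose finding or safety stopping is distorted.* Dose-limiting toxicities (7.213) and the stopping rule (16.532) need high grades and at least possible attribution. An unchanged entry condition meeting both is unlikely.
- *That the tables would mislead more often than not.* At 15% carry-over the chance in the second table is 65% at p = 10% but 27% at p = 30%, and nothing in the documents says that carry-over reaches 15%.
- *That the translational comparisons lose power.* Adverse event incidence is undefined there, the analyses are exploratory, and no power is stated for that outcome.

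**Conclusion.** The point holds as a gap in the descriptive safety analysis. The plan collects baseline grades and then states table rules that do not use them. Following those rules can count unchanged low-grade entry conditions, on solicited items, as adverse events of the regimen.

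The amount is unknown. At p = 10% it ranges from about 2 percentage points (q = 10%, r = 0.25) to 45 (q = 50%, r = 1), and every q and r is an assumption. Attribution offsets part of it, but with no stated rule. The primary endpoint does not depend on adverse event grading. Grade 3-5 rates are essentially unaffected, because few patients who meet Section 3 should enter with a solicited item already at that grade. This is a worthwhile, inexpensive improvement and not a threat to the trial's conclusions.

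**What to change.** Add to Sections 16.52 and 16.21:

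- For solicited items, tabulate per patient the maximum grade after the first dose of study drug among events that are new, of higher grade than baseline, or recurring after documented resolution. Give this for all such events and for those at least possibly related.
- Show the planned maximum grade regardless of baseline beside it.
- For diarrhea, use the baseline stool count as the reference.
- Use the same definition for adverse event incidence in the exploratory translational analyses.

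Counting should start at first dose and not at registration, because Section 6.36 allows an interval of days between the two and changes before dosing would otherwise count as new. The recurrence clause keeps events that resolve and return on drug at their entry grade. A table of baseline against maximum grade for laboratory items is optional.

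The cost is a few extra columns in the safety tables and minor programming. No new data, visits or patients are needed.

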16.53 Data & Safety Monitoring

- 16.531 The principal investigator(s) and the study statistician will review the study at least twice a year to identify accrual, adverse event, and any endpoint problems that might be developing. The Mayo Clinic Cancer Center (MCCC) Data Safety Monitoring Board (DSMB) is responsible for reviewing accrual and safety data for this trial at least twice a year, based on reports provided by the MCCC Statistical Office.
- 16.532 Adverse Event Stopping Rule (PHASE II ONLY): The stopping rule specified below is based on the knowledge available at study development. We note that the Adverse Event Stopping Rule may be adjusted in the event of either (1) the study re-opening to accrual or (2) at any time during the conduct of the trial and in

consideration of newly acquired information regarding the adverse event profile of the treatment(s) under investigation. The study team may choose to suspend accrual because of unexpected

adverse event profiles that have not crossed the specified rule below.

Accrual will be temporarily suspended to this study if at any time we observe events considered at least possibly related to study treatment (ie, an adverse event with attribute specified as "possible", "probable", or "definite") that satisfy the following:

• if 3 or more patients in the first 20 treated patients (or 10% after 20 patients have been accrued) experience a Grade 4 or higher non-hematologic adverse event.

We note that we will review Grade 4 and 5 adverse events deemed "unrelated" or "unlikely to be related", to verify their attribution and to monitor the emergence of a previously unrecognized treatment-related adverse event.

16.6 Results Reporting on ClinicalTrials.gov: At study activation, this study will have been registered within the "ClincialTrails.gov" website. The Primary and Secondary Endpoints (i.e., "Outcome Measures") along with other required information for this study will be reported on ClinicalTrials.gov. For purposes of timing of the Results Reporting, the initial estimated completion date for the Primary Endpoint of this study is 32 months after the study opens to accrual. The definition of "Primary Endpoint Completion Date" (PECD) for this study is at the time the last patient registered has been followed for at least 4 months.

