7.2 Phase I Dose Escalation and Determination of MTD

7.21 Dose Escalation Guidelines

| Dose Level | Auranofin |
|------------|------------|
| 0* | 3 mg daily |
| 1 | 6 mg daily |

^{*} Starting dose level.

- 7.211 Three patients will be treated at each dose level and observed for a minimum of 1 cycle, to assess toxicities, before new patients are treated.
- 7.212 Investigators are to contact the Study Chair as soon as any dose-limiting toxicity occurs.
- 7.213 For this protocol, dose-limiting toxicity (DLT) will be defined as an adverse event attributed (definitely, probably, possibly) in the first cycle to the study treatment and meeting the following criteria:

| Toxicity | DLT Definition |
|-------------|--------------------------|
| Hematologic | Grade 4 Neutropenia |
| | Grade 4 Thrombocytopenia |
| Non- | ≥Grade 3 Anaphylaxis |
| hematologic | |
| | ≥Grade 3 Proteinuria |
| | |
| | ≥Grade 3 Hematuria |
| | ≥Grade 3 Rash acneiform |
| | ≥Grade 3 Diarrhea |
| | ≥Grade 3 Mucositis oral |

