7.22 MTD Determination

MTD is defined as the dose level below the lowest dose that induces doselimiting toxicity in at least one-third of patients (at least 2 of a maximum of 6 new patients).

7.221 Three patients will be treated at a given dose level combination and observed for at least 1 cycle to assess toxicity (accrual will be suspended while the 3 patients are treated and observed).

- 7.222 If dose-limiting toxicity (DLT) is not seen in any of the 3 patients, 3 new patients will be accrued and treated at the next higher dose level. If DLT is seen in 2 or 3 of 3 patients treated at a given dose level, then the next 3 patients will be treated at the next lower dose level, if only 3 patients were enrolled and treated at this lower dose level.
- 7.223 If DLT is seen in 1 of 3 patients treated at a given dose level, up to 3 additional patients will be enrolled and treated at the same dose level (accrual will be suspended while the 3 patients are treated and observed). If DLT is seen in at least one of these additional three patients (≥2 of 6), the MTD will have been exceeded and further accrual will cease to this cohort. If DLT is not seen in any of the three additional patients, 3 new patients will be accrued and treated at the next higher dose level.
- 7.224 After enrolling 6 patients on a specific dose level, if DLT is observed in at least 2 of 6 patients, then the MTD will have been exceeded and defined as the previous dose unless only 3 patients were treated at the lower dose level. In that case, 3 additional patients will be treated at this lower dose level.
- 7.23 Dose Escalation: Doses will not be escalated in any individual patient.
- 7.24 If a patient fails to complete Cycle 1 for reasons other than toxicity, the patient will be regarded as treatment intolerant and an additional patient will be treated at the current dose level.
- 7.3 Patients can be instructed in administration techniques for both sirolimus and auranofin and granted treatment independence.
- 7.4 Patient must return to Mayo Clinic for evaluation at least every week during the first cycle of treatment and then at least every 4 weeks.
- 7.5 Study treatment by a local medical doctor (LMD) is not allowed.

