Dermatologic: Generalized exfoliative dermatitis, angioedema

Gastrointestinal: Dysphagia, gastrointestinal bleeding,

melena, positive stool for occult blood, ulcerative enterocolitis

Mucous membrane: Gingivitis

Hematologic: Aplastic anemia, neutropenia, agranulocytosis, pure

red cell aplasia, pancytopenia

Hepatic: Jaundice

Neurologic: Peripheral neuropathy Respiratory: Interstitial pneumonitis

15.18 Drug procurement:

Commercial supplies. Pharmacies or clinics shall obtain supplies from normal commercial supply chain or wholesaler.

15.19 Nursing Guidelines:

- 15.191 Auranofin is contraindicated in patients with history of gold-induced disorders (see section 15.17). Assess patients for any of these conditions, hold drug and notify study team.
- 15.192 Dermatitis is common and is exacerbated by sunlight. Instruct patients to avoid prolonged sun exposure without protection (i.e sunscreen SPF 30+ and covering up with clothing).
- 15.193 Patients may experience hair loss. Warn patients of this possibility.
- 15.194 Gastrointestinal side effects are common (diarrhea, constipation, nausea, vomiting, etc.) Treat symptomatically and assess for effectiveness.
- 15.195 Monitor LFT's as elevated liver enzymes have been seen. Report elevations to study physician.
- 15.196 Cytopenias can be seen. Rarely these can be serious. Monitor CBC w/differential. Instruct patients to report any excessive bruising or bleeding and/or signs/symptoms of infection to study team.
- 15.197 Instruct patients to report any hematuria to the study team.
- 15.198 Pneumonitis has been reported rarely, but can be serious and life-threatening. Instruct patients to report any cough, shortness of breath, and/or chest pain to the study team immediately.

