16.11 Phase I Study

This run-in phase I study is a cohorts of 3 design. For a subject to be considered evaluable for dose-limiting toxicity (DLT) the subject must have received at least one dose of each drug in Cycle 1. If a subject withdraws from the study within the first cycle of treatment for reasons other than adverse events, the subject will be replaced; and only DLTs occurring in Cycle 1 will be used for establishing safety during the run-in phase I study. However, all adverse event data will be summarized in the final analysis. For this run-in phase I study, DLT the study design is defined in Section 7.0. The patients treated at the MTD within the phase I will be included in the phase II efficacy analysis. Safety for all patients (including the patients in the run-in phase I study) will continue to be monitored via the Adverse Event Stopping Rule.

- 16.12 Sample Size: Phase I: The study may involve a maximum of 12 patients (6 for each of 2 dose levels). Phase II: This study will accrue an additional 35 patients to have a total of 41 patients accrued to the efficacy portion of this study (6 patients at the MTD in the phase I portion plus 35 patients accrued during the phase II portion). This includes 10% overaccrual of patients during the phase II portion to allow for cancellation, ineligibility, and major treatment violations (i.e., accrual of 41 patients to have 37 evaluable patients as required in 16.41). Overall: Therefore, overall, the study will accrue a maximum of 47 patients.
- 16.13 Accrual Time and Study Duration: The anticipated accrual rate is approximately 2 patients per month, based on physician estimate. This corresponds to a requirement of approximately 17 weeks to enroll (12 weeks), treat (4 weeks), and evaluate (1 week to submit data) 6 patients. Therefore, the accrual time for the phase I portion will be a maximum of 34 weeks. The overall study duration will be 34 weeks (phase I component) + 70 weeks (accrual of an additional 35 patients) + 16 weeks (4 months to evaluate the primary endpoint) = 120 weeks (about 28 months). The final analysis can begin approximately 28 months after activation, i.e., as soon as the last patient has been observed for 4 months and data have been submitted.

16.14 Operating Characteristics: The following table gives the probability of dose escalation at a single dose level as a function of the true probability of DLT at that level using the cohorts of 3 design described in Section 7.0.

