| True Rate of DLT (%) | Probability of Dose Escalation |
|----------------------|--------------------------------|
| 10 | 0.91 |
| 20 | 0.71 |
| 30 | 0.49 |
| 40 | 0.31 |
| 50 | 0.17 |

16.2 Phase I Analysis Plans: All the relevant phase I results pertaining to adverse events, MTD, clinical endpoints, and laboratory correlates will be examined in an exploratory and hypothesis generating fashion.

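### The automatic phase II suspension trigger (16.532) leaves out all hematologic events and all Grade 3 non-hematologic events, although both kinds can be dose-limiting in phase I (7.213)

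*Combined protocol and SAP*

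**What the plan says.** **Phase II trigger (16.532).** The threshold for a temporary suspension of accrual reads "if 3 or more patients in the first 20 treated patients (or 10% after 20 patients have been accrued"). The patients counted toward this threshold are those who "experience a Grade 4 or higher non-hematologic adverse event", provided that the event is at least possibly related to treatment. No operating characteristics are given for this rule.

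**Phase I yardstick (7.213, 7.22).** The DLT table has eight terms. Two are hematologic: "Grade 4 Neutropenia" and Grade 4 thrombocytopenia. Six are non-hematologic and start at Grade 3: anaphylaxis, proteinuria, hematuria, acneiform rash, diarrhea and oral mucositis. The MTD is the level below the "lowest dose that induces doselimiting toxicity in at least one-third of patients".

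**Known toxicity (15.17, 15.27).** The rare but important auranofin risks include "Hematologic: Aplastic anemia, neutropenia, agranulocytosis". For sirolimus, thrombocytopenia and leukopenia are listed.

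**Other safety provisions.** In 16.532 the study team may suspend accrual below the threshold for unexpected adverse event profiles, and the rule may be adjusted during the trial. The DSMB reviews safety data at least twice a year (16.531). Adverse events may inform a decision to terminate (16.43). Section 10.2 requires a written report of Grade 3 to 5 events within 5 working days.

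**Scope.** The heading in 16.532 reads "Adverse Event Stopping Rule (PHASE II ONLY"), whereas 16.11 says that safety for all patients, run-in patients included, "will continue to be monitored via the Adverse Event Stopping Rule".

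**The concern.** Phase I settles the dose on three to six patients per level, so a dose above the plan's own toxicity limit can reach phase II by chance. Phase II adds 35 patients and is where such a mistake should show. The plan changes its yardstick between the phases without giving a reason. Events that would have stopped escalation in phase I need not register on the only numeric trigger in phase II. If toxicity at the chosen dose is mainly marrow suppression or Grade 3 non-hematologic events, accrual could continue at a DLT rate of one-third or more with no stated boundary crossed.

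**Working it through.** **1. Coverage of the DLT terms by the trigger**

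| 7.213 term | Counted by 16.532? |
|---|---|
| Grade 4 neutropenia | No |
| Grade 4 thrombocytopenia | No |
| Six non-hematologic terms, Grade 3 | No |
| The same six terms, Grade 4 or higher | Yes, if at least possibly related |

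Two of the eight terms are wholly outside the trigger and six are partly inside. A related Grade 5 hematologic event also falls outside it.

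**2. The plan's own figures.** The table headed "Probability of Dose Escalation" in 16.14 follows from P = (1−p)³ + 3p(1−p)⁵.

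| True DLT rate p | Computed | Stated |
|---|---|---|
| 10% | 0.906 | 0.91 |
| 20% | 0.709 | 0.71 |
| 30% | 0.494 | 0.49 |
| 40% | 0.309 | 0.31 |
| 50% | 0.172 | 0.17 |

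All five reproduce. At p = 1/3 the formula gives 0.43. These are the chances of passing one level, not of entering phase II at it. Section 16.12 assumes six patients at the MTD. If all six are treated, P(at most 1 DLT in 6) = (1−p)⁶ + 6p(1−p)⁵. At p = 1/3 this is 0.088 + 0.263 = 0.35, and at 40% it is 0.23. Either way, a dose at or above the one-third limit has an appreciable chance of being carried forward.

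**3. The present rule at a one-third DLT rate.** Let s be the share of affected patients who have a Grade 4+ non-hematologic event. The documents do not give s, so a range is shown. The rate counted is s/3. The first result column is the binomial P(at least 3 of 20). The second is an exact patient-by-patient recursion to 41 patients (6 at the MTD plus 35, from 16.12), crossing at 3 or more events up to patient 20 and at 10% or more of patients after that.

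| s | Rate counted | P(≥3 of 20) | P(crossed by 41) |
|---|---|---|---|
| 0% | 0 | 0 | 0 |
| 10% | 0.033 | 0.03 | 0.09 |
| 25% | 0.083 | 0.23 | 0.52 |
| 50% | 0.167 | 0.67 | 0.94 |
| 100% | 0.333 | 0.98 | >0.999 |

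At that DLT rate, about 41/3 ≈ 14 of the 41 patients would be affected.

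**4. Why simply widening the present rule is not the answer.** With all 7.213 events counted against the existing cut-offs, the same recursion crosses by 41 patients with probability 0.66 at a 10% DLT rate and 0.98 at 20%. Both rates are below the plan's one-third limit, so a separate boundary is needed.

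**5. An illustrative boundary on 7.213 events.** Suspend at 5 or more events up to patient 12, at 7 or more up to patient 20, and after that at the larger of 7 and one-third of the patients treated, rounded up. Two populations are shown: 35 new patients, and 41 patients including the six at the MTD. The second is conditional on at most one DLT among those six.

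| True DLT rate | 35 new patients | 41, including the six |
|---|---|---|
| 10% | 0.007 | 0.002 |
| 15% | 0.05 | 0.02 |
| 20% | 0.16 | 0.07 |
| 33% | 0.73 | 0.56 |
| 40% | 0.91 | 0.81 |

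The two columns differ materially, so any stated operating characteristics must match the patients whom the rule counts.

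**The case against.** The strongest reply is that the trigger is not the only safeguard. The team may suspend below the threshold, the rule can be adjusted, the DSMB sees all safety data, and 16.43 lets adverse events inform termination. Section 8 requires delay and dose reduction for individual patients, counts are checked weekly in cycle 1, and serious events are reported within days. A cycle-1 DLT and an all-cycle accrual trigger serve different purposes, so some difference in criteria is a legitimate design choice.

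Much of this stands, and it rules out several stronger readings:

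- A reader might infer that the omitted events can never suspend accrual. They cannot trip the automatic rule, but the discretionary routes remain.
- A reader might infer that most dose-limiting events are excluded. Only two of eight terms are wholly excluded, and the documents give no event frequencies.
- Fatal marrow toxicity is not itself a listed DLT. The hematologic rows name only Grade 4 neutropenia and thrombocytopenia, and 15.17 puts aplastic anemia among toxicities below 1%. A death during neutropenia that is coded as infection might count as non-hematologic, because the boundary between the two classes is not defined.

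The safeguards do not close the gap. The discretionary clause speaks of unexpected profiles, and 10.12 defines unexpected as not listed in Section 15. Neutropenia, thrombocytopenia, proteinuria, hematuria, diarrhea and stomatitis are all listed there, so they are expected by the plan's own definition. At about 2 patients a month (16.13), six months between DSMB reviews allows 2 × 6 = 12 enrolments. The extra Grade 4 and 5 review in 16.532 covers only events judged unrelated or unlikely to be related. Reporting and patient-level dose rules set no limit on accrual.

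**Conclusion.** The point holds for the automatic trigger: it does not match the plan's own definition of dose-limiting toxicity, and nothing in phase II tests the one-third criterion numerically. How much this matters depends on the type of toxicity. At a one-third DLT rate, the chance that the present rule fires by 41 patients runs from 0, if no affected patient has a Grade 4+ non-hematologic event, through 0.09 and 0.52, to 0.94 if half of them do. The zero is the extreme of an assumed range, not a property of the trial, and a reader should not take it as the expected performance. The calculation assumes independent patients with a constant event rate, all six MTD patients counted, and suspension at 10% or more after patient 20. This is a worthwhile safety improvement at low cost. It does not show that the trial lacks safety oversight.

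**What to change.** 1. Keep the present rule in 16.532.
2. Count any at least possibly related Grade 5 event toward it, whether hematologic or not. Such a death would be one event toward the threshold and would not by itself suspend accrual.
3. Reconcile 16.532 with 7.213 and 7.22 by adding an accrual-monitoring boundary on 7.213 events tied to the one-third criterion, or else justify the difference. The sponsor should set the cut-offs and say whether events after cycle 1 count. The boundary in the working is an illustration only.
4. Resolve the scope conflict between 16.11 and the heading of 16.532, so that it is clear whether the six MTD patients count.
5. State operating characteristics for both boundaries, computed for the patients actually counted.

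**Cost.** This takes about a paragraph of text. The data are already collected through cycle-1 laboratory monitoring and the reporting of Grade 3 and 4 events. The downside is an occasional needless temporary suspension. Under the illustrative boundary, at a 15% true DLT rate, its probability is 0.05 over 35 new patients, or 0.02 over 41 including the six. At 20% it is 0.16 or 0.07.
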